7.3.5 Sponsor Responsibility for Reporting Adverse Events

All Adverse Events will be reported to regulatory authorities, IRB/IECs and investigators in accordance with all applicable global laws and regulations.

8.0 STATISTICAL ANALYSIS PLAN

8.1 Statistical Analysis Plan Summary

This is a phase II study to evaluate the efficacy and safety of pembrolizumab+p53MVA vaccine in advanced ovarian cancer who have progressed after at least one line of chemotherapy for advanced disease and are resistant to platinum therapy.

The primary endpoint in this trial will be response rate (CR+PR).

Secondary endpoints include median PFS, median OS and clinical benefit (CR+PR+SD>6 months), safety and tolerability, and biological correlates which remain exploratory in nature. Median PFS and OS will be reported in months. Clinical benefit will be calculated as the % of patients experiencing CR or PR or SD in total. Response rate, clinical benefit, PFS, and OS will also be summarized by PDL-1 expression.

8.2 Statistical Analysis Plan

Sample Size Accrual Rate

Study size is based on our therapeutic target of achieving with acceptable toxicity a considerable improvement in the response rate observed with single agent pembrolizumab in this patient population, previously reported as 8% (KEYNOTE-100). Specifically, we seek to have good power to detect an improvement in the response rate to 25%. To achieve this, Simon's MiniMax two-stage design is employed to have 85% power to detect a true promising response rate of 25%, with a type I error of 8% for declaring a true discouraging response rate of 8% as worthy of further consideration: Initially, 17 patients will be enrolled for the first stage. If 2 or more patients experience a response during the first stage, accrual will continue to 28 patients. With a total of 28 patients, at least 5 responders (18%) is the minimum to determine the combination worthy of further consideration. This design has a 60% chance of early stopping if the true response rate is 8%. Final determination of promise will be based on the totality of the clinical endpoints and consideration of the profile of patients' PDL-1 expression, where a different accrual pattern when compared to KEYNOTE-100 may require a higher or lower threshold for the final decision. Expected accrual rate is approximately one patient every one and ½ months.

Analysis of Biological Correlates

Peripheral blood samples will be collected pre- and post-immunization for assessment of anti-p53 T cell responses and immunophenotyping. Immunosuppressive cell types (MDSC, Tregs) and other selected lymphocyte subsets and markers including PD-1, PDL-1 and PDL-2 will be quantified. Secondary endpoints will be clinical responses and T cell reactivity to p53. These

secondary endpoints are exploratory in nature. We will evaluate if the CD8⁺ T cell signal exceeds that detected in the single agent p53MVA trial. In the prior single agent study the p53-reactive CD8⁺ T cells increased above baseline after the first immunization, but did not expand further with subsequent immunization. We hypothesize that the CD8⁺ T cell response will be enhanced by pembrolizumab, resulting in larger or more durable increases in the CD8⁺ T cell response. The total area under the curve (AUC) of the CD8⁺ T cell reactivity over three injections (minus the baseline) provides a metric for this requirement. We have approximately 84% power to detect a 2.1-fold increase in AUC with a type I error of 22%. Empirically, this is associated with a cut-off of a 55% increase in AUC. These estimates use the Wilcoxon rank-sum test, and are based on residual re-sampling simulations based on historical AUC values (subtracting baseline) and a hypothesized increase in that AUC.

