 - Patients with documented disease recurrence/progression within 6-12 months of completing platinum-based therapy, are considered to have 'borderline' platinum sensitivity. **These patients will not be eligible for this trial.**

- Patients who relapse more than 12 months after completion of platinum-based treatment are considered ‘platinum sensitive’ and **will not be eligible for this trial**, since they have a favorable (33-59%) chance of responding to further rounds of platinum based chemotherapy.

5. Patients with confirmed p53 mutation by molecular analysis and/or evidence of p53 overexpression by immunohistochemistry ($\geq 10\%$ of cells within the tumor staining positive) will be eligible. This will be assessed semi-quantitatively by a CLIA approved Pathology Core Pathologist, using CLIA approved mutational analysis or immunohistochemistry techniques on formalin-fixed paraffin-embedded tissue. In the case of equivocal IHC results, p53 involvement may be confirmed by detection of p53 molecular analysis on tumor DNA. Patients on whom molecular analysis of p53 mutations is already available, will not require ICH analysis. Molecular analysis may be performed as an additional research procedure at the end of the study (distinct from eligibility determination) if the PI deems it of scientific value and research funding is available to cover the cost. Patients are not required to have PD-L1 positive ovarian tumors and PD-L1 testing is not mandatory on this study. However, we will collect the data on PD-L1 testing when available.
6. Have an Eastern Cooperative Oncology Group (ECOG) performance status of ≤ 2 (Karnofsky $\geq 60\%$) and a life expectancy of at least 3 months.
7. Up to 4 prior chemotherapy regimens for recurrent disease are allowed. Adjuvant chemotherapy and maintenance Taxol after completion of six cycles of adjuvant Carboplatin – Taxol will not be counted as a “prior chemotherapy regimen” for the purpose of this study. Treatment with targeted agents or hormones would not be considered as a systemic chemotherapy regimen. Eligible Patients are those with documented disease recurrence/progression within 0-6 months of completing platinum-based chemotherapy. Patients should not have received any non-oncology, viral vaccines within 30 days prior to starting protocol treatment.
8. Have adequate organ function as defined in the following table (Table 1). Specimens must be collected within 14 days prior to the start of study treatment.

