7.1.2 Clinical Assessments

The following laboratory tests will be conducted at baseline and during the treatment phase according to the study chart:

- a. Complete blood count with platelet count and differential
- b. Comprehensive metabolic panel
- c. Urine for pregnancy test where appropriate
- d. Blood for immune studies which will be processed and stored by [name] Lab. PBMC will be separated from heparinized blood by standard density gradient centrifugation and analyzed immediately, or cryopreserved for future analysis.
- e. Serum Troponin (I) and B-type natriuretic peptide (BNP)
- f. Immuno-histochemistry staining for the primary ligand of PD-1 (PDL-1)
- g. CA-125 tumor marker

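### Section 8.2 lets the final response cut-off move with PD-L1 mix without a mapping, limit or time of fixing, so the stated 8% and 85% together do not describe the decision rule as written

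*Combined protocol and SAP*

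**What the plan says.** All of the decision text sits in one paragraph of Section 8.2 (Sample Size Accrual Rate). It describes a Simon minimax design with 85% power at a true response rate of 25%, "with a type I error of 8% for declaring a true discouraging response rate of 8" per cent. Stage 1 enrols 17 patients and the trial continues if 2 or more respond. At 28 patients, "at least 5 responders (18%) is the minimum to determine the combination worthy of further consideration".

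The paragraph then adds that "Final determination of promise will be based on the totality of the clinical endpoints" and on the patients' PD-L1 profile, "where a different accrual pattern when compared to KEYNOTE-100 may require a higher or lower threshold for the final decision".

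Elsewhere:

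- Section 8.1 plans summaries: "Response rate, clinical benefit, PFS, and OS will also be summarized by PDL-1 expression".
- Section 4.2 reports that KEYNOTE-100 scored PD-L1 by CPS and that CPS of 10 or more had a higher response rate than CPS of 1 or more or below 1. The readable text gives neither that study's PD-L1 distribution nor its response rates by category.
- Section 5.1.1, item 5, says that "PD-L1 testing is not mandatory on this study", and that "we will collect the data on PD-L1 testing when available".
- Section 9.3 states that the trial is open-label.

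**The concern.** A two-stage design earns its error rates from a cut-off fixed before the data are seen. Here the paragraph that states the rates also allows the final cut-off to change. It calls 5 responders the minimum and then allows a lower threshold, so the two statements conflict and the minimum does not act as a limit.

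The information that could move the threshold, the PD-L1 profile, accrues alongside the responses, and nobody is blinded. Nothing says when the comparison with KEYNOTE-100 is made, how different the mix must be, how many responders a given difference is worth, or what happens with untested patients. A total of 4 or 5 responders could then be read either way once it is known, provided the mix is judged different. A reader of the final report would have no written rule against which to check a moved threshold.

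**Working it through.** **Inputs.** From Section 8.2: null rate 8%, target 25%, n1 = 17, continue if X1 ≥ 2, N = 28 (so 11 patients in stage 2), final cut-off r = 5. From Section 4.2, for sensitivity only: avelumab response rates of 5.9% (PD-L1 negative) and 12.3% (PD-L1 positive).

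**Formula.** With X1 ~ Bin(17, p) and X2 ~ Bin(11, p):

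P(declare | p, r) = Σ over x ≥ 2 of P(X1 = x) × P(X2 ≥ r − x)

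**Step 1: reproduce the plan's figures (r = 5).**

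- Early stopping at 8%: 0.92^17 + 17 × 0.08 × 0.92^16 = 0.2423 + 0.3582 = 0.6005 (stated 60%).
- Type I error at 8%: x = 2: 0.24919 × 0.05190 = 0.01293; x = 3: 0.10834 × 0.21810 = 0.02363; x = 4: 0.03297 × 0.60036 = 0.01980; x ≥ 5: 0.00895. Sum 0.0653, within the 8% limit.
- Power at 25%: 0.06188 + 0.15200 + 0.21154 + 0.42611 = 0.8515 (stated 85%).

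An exhaustive minimax search with type I error ≤ 8% and power ≥ 85% returns the same 17/28 design. The 8% is the limit used to choose the design; 6.5% is what the rule attains. There is no calculation error.

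**Step 2: move the final cut-off, with the null kept at 8% and stage 1 unchanged.**

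| Final cut-off | Type I error at 8% | Power at 25% | Meets ≤ 8% and ≥ 85%? |
|---|---|---|---|
| 4 | 16.1% | 92.0% | No (type I error) |
| **5** | **6.5%** | **85.2%** | **Yes** |
| 6 | 2.1% | 73.1% | No (power) |
| 7 | 0.55% | 57.1% | No (power) |

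**Step 3: how often a one-responder shift matters.** It can change the call only if the trial reaches stage 2 and ends with 4 or 5 responders.

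- At 8%: 0.0960 + 0.0444 = 0.1404, or 14.0% of trials. Among trials reaching stage 2: 0.1404 / 0.3995 = 35.1%.
- At 25%: 0.0680 + 0.1205 = 0.1884 (from unrounded terms), or 18.8% of trials. Among trials reaching stage 2: 0.1884 / 0.9499 = 19.8%.

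**Step 4: let the null move with the mix.** Type I error for each cut-off, taking the avelumab subgroup rates as illustrative nulls:

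| Null | Cut-off 4 | Cut-off 5 | Cut-off 6 | Cut-off 7 |
|---|---|---|---|---|
| 5.9% | 7.0% | 2.1% | 0.5% | 0.1% |
| 8% | 16.1% | 6.5% | 2.1% | 0.55% |
| 12.3% | 41.7% | 24.6% | 12.0% | 4.9% |

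Type I error stays within 8% for nulls up to about 6.2% (cut-off 4), 8.5% (cut-off 5) and 11.0% (cut-off 6). A different null can therefore justify a different cut-off. The documents do not supply the step from PD-L1 mix to null.

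**The case against.** The strongest reply is that the sentence reflects good sense. A single-arm trial judged against a historical rate depends on case mix, and a PD-L1-rich sample should face a higher bar. On that view the 16.1% describes a case the plan does not intend, since the threshold would drop only where the mix implies a lower benchmark; at a 5.9% null, cut-off 4 gives 7.0%. This stands: adjusting for mix is not in itself wrong. It does not supply the missing mapping or say when it is fixed.

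It can also be said that this is a 28-patient screen for further study, with a judgement on all endpoints openly declared. That limits the stakes, and the sentence may be meant only as a development judgement made after the statistical screen. But it speaks of the threshold for the final decision and sits in the paragraph that quotes the error rates.

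Three stronger readings are tempting and are not supported:

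- *That the stated rates fail at every other cut-off.* They fail only as a pair. Type I error is also within 8% at cut-offs 6 and 7, and power also exceeds 85% at cut-off 4.
- *That 4 of 28 could always be called promising, or 5 of 28 rejected, under the threshold sentence.* That sentence makes a shift conditional on a PD-L1 pattern different from KEYNOTE-100. With a similar mix, lowering the bar to 4 would contradict the stated minimum.
- *That no reference exists.* KEYNOTE-100 is named and Section 4.2 gives its CPS categories. The proportions may lie in the cited report or in a figure that is not readable here.

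The PD-L1 testing question is secondary. Section 7.1.2 lists PD-L1 staining among tests done according to the study chart, but the chart in Section 6.1 has no such row, which favours the optional reading in Section 5.1.1.

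**Conclusion.** The point holds in a limited form and should be fixed. The two-stage design is correctly calculated. What is not settled is the rule for the final call: the text contradicts itself on whether 5 is a floor, and it leaves the cut-off open to change after responses are known whenever the mix is judged different. The 8% and 85% together therefore do not describe the decision rule as written.

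If the null is in fact 8%, a one-responder move costs either about a doubling of the type I error limit (16.1% against 8%) or about 12 points of power (73.1% against 85%). These are consequences of particular shifts, not estimates of the trial's actual error rate, which cannot be computed without a rule. They assume that the stage 1 rule is followed and that all 28 patients count in the denominator. The 5.9% and 12.3% nulls are illustrations from a different drug, and Section 4.2 reports the difference between them as not statistically significant. Nothing in the documents shows that the sponsor intends to choose the cut-off after seeing the results; the wording simply does not prevent it.

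**What to change.** Make at least 5 of 28 the fixed rule for the formal primary declaration. State that its 6.5% type I error assumes an 8% null and its 85.2% power a 25% rate. Reword the PD-L1 sentence so that PD-L1 mix, including the number untested, and the totality of endpoints are descriptive context for the later development decision and do not move the formal threshold. This also removes the conflict with the stated minimum.

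The cost is SAP wording. The downside is that a fixed rule does not adapt to case mix, so the result should be shown beside the PD-L1 mix, with the type I error over a range of nulls (for illustration, 2.1% at 5.9% to about 24.6% at 12.3%).

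An equally good alternative, if PD-L1 results will be available for most patients, is to keep the adjustment and write it down before any response is assessed: assay and categories, reference mix, benchmark rate for each category, the mapping from mix to cut-off, the handling of untested patients, and the type I error and power of each resulting rule. This costs near-complete testing and a source for the benchmark rates.

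Under either option, reconcile Sections 5.1.1, 6.1 and 7.1.2 on whether tumor PD-L1 is tested.

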9.0 LABELING, PACKAGING, STORAGE AND RETURN OF CLINICAL SUPPLIES

9.1 Investigational Product

The investigator shall take responsibility for and shall take all steps to maintain appropriate records and ensure appropriate supply, storage, handling, distribution and usage of investigational product in accordance with the protocol and any applicable laws and regulations.

Pembrolizumab will be provided by Merck as summarized in Table 8.

Table 8 Product Descriptions

Product Name & Potency	Dosage Form
Pembrolizumab 100 mg/ 4mL	Solution for Injection

9.2 Packaging and Labeling Information

Supplies will be labeled in accordance with regulatory requirements.

9.3 Clinical Supplies Disclosure

This trial is open-label; therefore, the participant, the trial site personnel, the Sponsor and/or designee are not blinded to treatment. Drug identity (name, strength) is included in the label text; random code/disclosure envelopes or lists are not provided.

9.4 Storage and Handling Requirements

PEMBROLIZUMAB

Clinical supplies must be stored in a secure, limited-access location under the storage conditions specified on the label. Receipt and dispensing of trial medication must be recorded by an authorized person at the trial site. Clinical supplies may not be used for any purpose other than that stated in the protocol.

Preparation: Add 2.3 mL of Sterile Water for Injection, USP by injecting the water along the walls of the vial (not directly on the lyophilized powder), resulting in a concentration 25 mg/ml. Slowly swirl the vial. Allow up to 5 minutes for the bubbles to clear. Do not shake the vial. Visually inspect the reconstituted solution for particulate matter and discoloration prior to administration. Reconstituted pembrolizumab is a clear to slightly opalescent, colorless to slightly yellow solution. Discard reconstituted vial if extraneous particulate matter other than translucent to white proteinaceous particles is observed. Alternatively, pembrolizumab solution provided at 100mg/4mL (25mg/mL) will be used.

Withdraw the required volume from the vial(s) of pembrolizumab and transfer into an intravenous (IV) bag containing 0.9% Sodium Chloride Injection, USP. Mix diluted solution by gentle inversion. The final concentration of the diluted solution should be 1 mg/mL - 10 mg/mL and administered IV over 30 minutes, through an intravenous line containing a sterile, non-pyrogenic, low-protein binding 0.2 micron to 5 micron in-line or add-on filter.

Storage of Reconstituted and Diluted Solutions: pembrolizumab contains no preservative, hence reconstituted, diluted solutions should not be stored at room temperature for more than 6 hours after preparation. This includes storage of reconstituted vials, storage of infusion solutions in the IV bag and the duration of infusion. Under refrigeration (2°C - 8°C) diluted solutions should not be stored for more than 24 hours from the time of preparation. If refrigerated, allow the diluted solution to come to room temperature prior to administration. Do not freeze. Caution should be exercised in handling pembrolizumab solutions. The use of gloves and gowns is recommended. If the product comes into contact skin or mucosa, the skin should be washed thoroughly with soap and water and mucosa irrigated with copious amounts of water.

Disposal: Unused and residual drug should be put into a plastic bag and disposed of in a chemical waste container.

p53MVA Vaccine (IND#14716)

p53MVA is a Modified Vaccinia Ankara Virus based vaccine expressing the full length, wild type human p53 gene. The p53MVA vaccine was evaluated in an FDA directed toxicology study in mice. p53MVA was administered doses 50 fold higher, in a mg/kg basis, than the proposed starting clinical dose. There was no obvious toxicity seen in the animals in terms of weight, physical appearance, activity level, chemical or hematologic parameters. Histologic evaluation of organs at necropsy revealed no evidence of toxicity. p53MVA was cleared from the skin injection site within 60 days of administration and from all other tissues including blood within 2 weeks of administration. In the first in human study conducted at COH, the

p53MVA vaccine was been well-tolerated at doses of 1×10^8 pfu and 5.6×10^8 pfu with only low grade toxicity being reported.

p53MVA has been manufactured using GMP-grade materials at The Center for Biomedicine and Genetics (CBG) at City of Hope. The final product is diluted in PBS with 7.5% lactose and vialed at 1.2ml per vial. The concentration is 4.5×10^8 pfu/ml. The vaccine is expected to remain stable at room temperature for a minimum of 4 hours, as determined in recently completed stability study stipulated by the FDA. Patients will receive injections of 1.1ml for dose level 1. In the event of de-escalation to dose level -1, patients will receive an injection volume of 0.5ml, giving a dose of 2.2×10^8 pfu.

9.5 Returns and Reconciliation

The investigator is responsible for keeping accurate records of the clinical supplies received from Merck or designee, the amount dispensed to and returned by the participants and the amount remaining at the conclusion of the trial.

Upon completion or termination of the study, all unused and/or partially used investigational product from Merck will be destroyed at the site per institutional policy. It is the Investigator's responsibility to arrange for disposal of all empty containers, provided that procedures for proper disposal have been established according to applicable federal, state, local and institutional guidelines and procedures, and provided that appropriate records of disposal are kept.

All unused (unopened) vials of p53MVA vaccine will be stored at COH IDS, or returned to the CBG, as per the PI direction.

10.0 ADMINISTRATIVE AND REGULATORY DETAILS

10.1 Institutional Review Board

In accordance with City of Hope policies, an Institutional Review Board (IRB) that complies with the federal regulations at 45 CFR 46 and 21 CFR 50, 56 and State of California Health and Safety code, Title 17, must review and approve this protocol and the informed consent form prior to initiation of the study. All institutional, NCI, Federal, and State of California regulations must be fulfilled.

10.2 Recruitment of Subjects

Individuals who satisfy the inclusion criteria will be identified through the individual practitioners in the Departments of General & Oncologic Surgery and Medical Oncology and Therapeutics Research at COH. Written informed consent will be obtained from the participant.

10.3 Advertisements

A lay summary to be posted on City of Hope's public Clinical Trials On-LineSM website and Clinicaltrials.gov will be reviewed and approved by the IRB prior to their use to recruit potential study subjects.

10.4 Study location and Performance Sites

This study will be performed at the City of Hope National Medical Center. All study interventions will be performed at this site by a study nurse under the direction of [name] or her designee at the Clinical Research Unit (Phase I unit) at COH. The laboratory analysis will take place in the Department of Experimental Therapeutics, [name] under the direction of [name].

10.5 Confidentiality

This research will be conducted in compliance with federal and state of California requirements relating to protected health information (PHI). The study will record individual immunological response to the vaccine and any side effects, and this will be linked to the subject's identity using a coded study number. The principal investigator, co-investigators, and laboratory technicians will have access to this information, but all information will be treated confidentially. No identifiers will be used in any subsequent publication of these results. Clinical information will not be released without written permission of the subject, except as necessary for monitoring by the FDA or NIH.

10.6 Financial Obligations and Compensation

The investigational agents, p53MVA and pembrolizumab, will be provided free of charge by COH according to the protocol.

Standard of care drugs and procedures will be the responsibility of the research participant and/or the insurance carrier. The research participant will be responsible for all copayments, deductibles, and other costs of treatment and diagnostic procedures as set forth by the insurance carrier. The research participant and/or the insurance carrier will be billed for the costs of treatment and diagnostic procedures in the same way as if the research participant were not in a research study. However, neither the research participant nor the insurance carrier will be responsible for the research procedures related to this study.

In the event of physical injury to a research participant, resulting from research procedures, appropriate medical treatment will be available at the City of Hope to the injured research participant, however financial compensation will not be available. The research participant will not be paid for taking part in this study.

